### 3.2.2.2.3 Diaries

**Exercise adherence diary**

Site staff should query the patient on adherence to the exercise program, [REDACTED] recorded in the exercise diary during the monthly telephone call. Exercise adherence diary at Week 25 will be summarized for both population I and population II, separately.

### **3.3 Treatments (study drug, other concomitant therapies, compliance)**

The analysis in this section will be based on SAF set.

For Population I, all summaries will be presented by treatment group in the extension study and overall. For Population II, all summaries will be presented by treatment assigned in the Core study and overall.

Relevant raw and derived data as described in this section will also be presented in by-patient data listings. All by-patient data listings will be sorted by Population, treatment group, [REDACTED] center and patient if not indicated otherwise.

Where relevant, “overall” refers to the addition of a “Total” treatment column within the planned presentation of the data.

#### **3.3.1 Study drug administration**

For Population 1, the analysis of study treatment data will be based on the safety analysis set. For each subject, cumulative exposure to study treatment will be calculated as the number of days of drug exposure=last infusion date - first infusion date + 56 days. The first infusion date refers to the first dose date following the last dose in the core study. The duration of exposure

to study drug will be summarized by treatment group, [REDACTED] as a continuous variable. The volume administered will also be summarized by visit and by treatment group as a continuous variable.

For Population 2, no exposure data will be presented.

### **3.3.2 Prior and concomitant medications**

Prior medications, concomitant medications ongoing at the entry of the extension study and concomitant medications initiated in the extension study will be summarized by treatment group in separate tables. Medications will be presented in alphabetical order, by ATC codes and grouped by *anatomical main group* (the 1st level of the ATC codes). Within ATC Level 1, the PTs will be sorted by descending frequency of the total number of patients with at least one medication in each PT. In the event of ATC categories and/or PTs with equal total frequencies, the relevant ATC categories and/or PTs will be sorted alphabetically. Tables will also show the overall number (n) and percentage (%) of subjects receiving at least one drug of a particular ATC code and at least one drug in a particular anatomical main group.

Summary by treatment group in this study will be provided for Populations I and II separately.

Prior medications are defined as drugs taken and stopped prior to first dose of study treatment for population I, or prior to the first visit (Week 25) in the extension study for population II. Any medication given at least once between the day of first dose of study treatment and the date of the last study visit for population I, or between the first visit (Week 25) in the extension study and the end of the study visit for population II, will be a concomitant medication, including those which were ongoing at the entry of the extension study and continued into the study. Prior or concomitant medication will be identified based on recorded or imputed start and end dates of medication taking. If it cannot be established that the use of a prior medication has ended prior to the first dose of study treatment due to a missing end date, then it will be considered concomitant. Algorithms for date imputations will be provided in RAP Module 8 (Programming Specifications).

## **3.4 Analysis of the primary variable(s)**

The primary analysis population for efficacy will be the Full Analysis Set.

The primary objective of this study is to assess the durability of effect of bimagrumab (BYM338) in older adults with sarcopenia as measured by the SPPB total score.

The primary endpoint is SPPB at week 49.

### **3.4.1 Descriptive statistics**

Descriptive statistics (i.e. N, mean, SD, median, 25th percentile, 75th percentile, minimum, maximum (not included for Interim Analysis), the number of non-missing observations, and 95% confidence intervals), per treatment, for each population separately, will be provided for the primary endpoint.

Longitudinal plots (Mean +/- SE), by treatment of observed values vs time profile will be produced, for each population separately.

### 3.4.2 Statistical model, hypothesis and method of analysis

For Population I, a 95% confidence interval for the difference in the primary endpoint between each continued BYM338 dose arm vs. corresponding placebo switched from the same BYM dose will be calculated at Week 49. The CI of the difference will be calculated using a t-test comparing the values at Week 49 between BYM338 dose arms vs. corresponding placebo. Summary statistics will also be presented by treatment arm.

For Population II, the summary statistics will be presented by treatment assigned in the core study.

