5.2 Treatment arms

Patients enrolled following protocol amendment #1 will not receive investigational treatment.

Patients enrolled prior to the protocol amendment #1 have been assigned to one of the following 2 treatment arms in a ratio of 1:1 to receive i.v. doses of the following and will continue with this treatment until their EOT:

1. Patients on BYM338 70 mg in core study were randomized 1:1 to receive either BYM338 70 mg or placebo (BYM 70/PBO) for 6 doses in the extension study
2. Patients on BYM338 210 mg in core study were randomized 1:1 to receive either BYM338 210 mg or placebo (BYM 210/PBO) for 6 doses in the extension study
3. Patients on BYM338 700 mg in core study were randomized 1:1 to receive either BYM338 700 mg or placebo (BYM 700/PBO) for 6 doses in the extension study
4. Patients on BYM338 0 mg (placebo) in core study were randomized 1:1 to receive BYM338 0 mg (placebo) in both arms for 6 doses in the extension study

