5.5 Treating the patient

5.5.1 Patient numbering

Patients in the extension study CBYM338E2202E1 will continue with the same uniquely identified patient number that was assigned in the core study.

As in the core study, the patient number is a combination of a four digit center number, which is provided by Novartis, and a three digit sequential number allocated by the investigator, starting with 001. Therefore, if the center number is 1001, the patient numbers will be assigned such as 1001001, 1001002, etc. in ascending order. If the center number is 1002, the patient numbers will be assigned such as 1002001, 1002002, etc.

Patients will be given the informed consent form (ICF) during one of the scheduled visits (e.g., Week 25 or at earlier visit) in study CBYM338E2202 to read and understand for their participation in this extension study. Patients will NOT be signing the ICF before completing the Week 25 (EOT) assessments of the core study.

Patients who are eligible based on the inclusion/exclusion criteria will be asked to sign the ICF. If the patient fails for any reason, he/she should not enter the extension and should complete the EoS visit of the core study as per the core study protocol.

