9.7 Sample size calculation

All the subjects from the core (CBYM338E2202), if eligible, can enter this extension study after they complete informed consent.

The standard deviation of SPPB can be found in the references in [Table 9-1](#), which are also referred by the core study protocol.

Table 9-1 Standard deviation of SPPB

Reference	Study description	SD
Perera et al (2006)	N=492 community dwelling adults	2.7 (Baseline)
Kwon et al. (2009)	N=424 older sedentary adults	1.42 (Baseline)
Papanicolaou et al (2013)	N=120 sarcopenic elderly women	1.48 (Baseline) 2.19 (After 6 months treatment)

1.93 (After 6 months placebo)

With 40 to 50 patients per each bimagrumab dose arm,, assuming a standard deviation of SPPB of 1.5, 2.0, 2.5, and 3.0, the half-width of 95% confidence interval for SPPB is presented below in [Table 9-2](#).

Table 9-2 Half-width of 95% confidence interval for SPPB

	SD=1.5	SD=2.0	SD=2.5	SD=3.0
50 patients per arm:	0.42	0.55	0.69	0.83
40 patients per arm:	0.46	0.62	0.77	0.93

10 Ethical considerations

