#### **3.5.3.1 6MWT, Gait speed, SPPB total score, total LBM and ASMI**

For population I, the 95% confidence interval will be provided for the difference between each continued BYM dose arm and corresponding placebo (switched from the same BYM dose arm) at each visit. 95% confidence interval will also be provided for the difference between each continued BYM dose arm and the placebo arm continued from the core study at each visit.

The confidence interval at Week 49 for SPPB total score between each continued BYM dose arm and corresponding placebo (switched from the same BYM dose arm) for population I is provided as the primary analysis. For population II, the summary statistics at Week 49 are provided as the primary analysis.

For population II, SPPB total score, 6MWT, Gait speed, total LBM and ASMI at Week 49 will be explored at final analysis using an analysis of variance model (ANCOVA) with treatment assigned in the core study [REDACTED] as fixed effects and Week 25 SPPB total score as covariate.

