## 5.4 Definition of Baseline and post-baseline measurements

Baseline is defined as the core study baseline, for both populations. In the planned analyses, Week 25 has been referred to majority of the time, and it is referring to a relative baseline to the extension study, which is defined as the Visit 1 pre-dose assessments of the extension study (Week 25, EOT visit of the core study) for population I and for population II defined as the Visit 1 assessments of the extension study (Week 25, EOT visit of the core). This visit will be labeled as Week 25 in the reports.

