## 5.8 Statistical methodology and assumptions

### 5.8.1 Two sample t-test

For Population I, the two-sample t-test will be used in order to obtain 95% confidence intervals for the difference between:

- each continued BYM338 dose arm vs. corresponding placebo, and
- Each continued BYM338 dose arm vs. continued placebo arm,

for the following endpoints:

- Week 25 to 49 on the 6MWT
- Week 25 to 49 on the SPPB
- Week 25 to 49 on the Gait speed
- Week 25 to 49 in log transformed values on LBM and ASMI

The t-test will assume Equal variances when the null hypothesis of variance equality cannot be rejected, and Unequal variances when the variance equality hypothesis is rejected.

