### 5.8.2 ANCOVA

For Population II, ANCOVA model is used to explore the durability of BYM338 on the following endpoints:

- Week 49 on the SPPB
- Week 49 on the 6MWT
- Week 49 on the Gait speed
- Week 49 in log transformed values on LBM and ASMI

[figure not shown]
The endpoint value at extension baseline as a covariate, treatment arm (as assigned in the core study for population II) [REDACTED] will be included as fixed effects. The 95% confidence intervals for the difference between arms receiving BYM338 and Placebo during the core study will be estimated.

[figure not shown]
[REDACTED]

[REDACTED]

[REDACTED]

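### The Population I primary interval leaves out the pre-randomisation Week 25 SPPB, so with about 4 to 6 patients per arm it is wider than needed if the two scores correlate at about 0.5 or more.

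*SAP*

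**What the plan says.** Population I is the group of about 45 patients enrolled before protocol Amendment 1. Protocol 5.2 describes a second randomisation within core arm; for the lowest dose, "Patients on BYM338 70 mg in core study were randomized 1:1 to receive either BYM338 70 mg or placebo". The 210 mg and 700 mg arms were split in the same way. The core placebo arm was also split, but both halves receive placebo.

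Protocol 9.4.1 and SAP 3.4 define the primary endpoint as SPPB at Week 49. For continued dose against the matching switched-to-placebo arm, SAP 3.4.2 states: "The CI of the difference will be calculated using a t-test comparing the values at Week 49 between BYM338 dose arms vs. corresponding placebo". Neither that section nor Protocol 9.4.2 names a covariate. SAP 5.8.1 adds a variance rule: "The t-test will assume Equal variances when the null hypothesis of variance equality cannot be rejected". SAP 3.5.3.1 applies the same method to the "difference between each continued BYM dose arm and the placebo arm continued from the core study".

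On the timing of the Week 25 value, Protocol 5.5.1 says: "Patients will NOT be signing the ICF before completing the Week 25 (EOT) assessments of the core study". SAP 5.4 treats Week 25 as the extension's own reference value, "which is defined as the Visit 1 pre-dose assessments of the extension study", and Protocol Table 6-2 lists SPPB at that visit. For Population II, SAP 5.8.2 does adjust: "The endpoint value at extension baseline as a covariate".

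**The concern.** Week 25 SPPB precedes the extension randomisation, so adjusting for it conditions on nothing that extension treatment can affect. It measures the same quantity as the endpoint, and it is already collected.

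The continued-versus-switched intervals are the only between-arm intervals in the primary analysis; Population II gets summaries by core arm. With so few patients per arm, precision is the main limit on what these intervals can show. Leaving the covariate out lets chance Week 25 differences between arms feed into the Week 49 comparison, in proportion to the correlation. The t interval allows for this by being wide, so the cost is width and not bias.

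A smaller, separate point is that SAP 5.8.1 lets a variance test choose the interval formula. That matters little for equal arms but can matter when arm sizes differ.

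**Working it through.** **The plan's own figure.** Protocol Table 9-2 (SAP Table 3-1) is 1.96 × SD / √n for one arm mean. For SD 1.5, 2.0, 2.5 and 3.0:
- n = 50 gives 0.4158, 0.5544, 0.6930, 0.8315 (printed 0.42, 0.55, 0.69, 0.83).
- n = 40 gives 0.4648, 0.6198, 0.7747, 0.9297 (printed 0.46, 0.62, 0.77, 0.93).

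All eight cells match. The table describes single arm means with 40 to 50 patients, not a Population I difference.

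**Arm size.** 45 / 8 = 5.6 per code. With the 30% dropout in Protocol section 4, 45 × 0.7 / 8 = 3.9. So n is about 4 to 6, assuming the core arms contribute equally. Continued placebo combines two codes, giving about 8 to 12.

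**Planned width.** The half-width is t(2n−2) × SD × √(2/n). At SD 2.0:
- n = 6: 2.228 × 2.0 × 0.577 = 2.57
- n = 5: 2.306 × 2.0 × 0.632 = 2.92
- n = 4: 2.447 × 2.0 × 0.707 = 3.46

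**Chance Week 25 imbalance.** The probability of a difference of at least 1.0 point (the relevant change in Protocol 6.3.2) is 2 × [1 − Φ(1 / (SD√(2/n)))]. For n = 6, 5, 4 this is 43%, 47%, 52% at SD 2.19 and 24%, 29%, 34% at SD 1.48. Both SDs are from Protocol Table 9-1.

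**Adjusting within each pair only.** The expected ratio to the planned width is about √(1−ρ²) × t(2n−3)/t(2n−2) × √(1 + 1/(2n−4)), where ρ is the Week 25 to Week 49 correlation. At ρ = 0 this is 1.175, 1.108, 1.077 for n = 4, 5, 6, because a degree of freedom is spent. Break-even ρ is 0.53, 0.43, 0.37 by the formula and 0.50, 0.41, 0.36 by simulation. Simulated ratios for n = 4, 5, 6 are 1.00, 0.95, 0.93 at ρ = 0.5 and 0.82, 0.78, 0.76 at ρ = 0.7.

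**Adjusting in one model over all seven arms.** The simulation used 20,000 runs per scenario, with HC2 standard errors and Bell-McCaffrey degrees of freedom. Mean half-widths at SD 2.0:

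| n per dose arm | SAP rule | ρ = 0 | ρ = 0.5 | ρ = 0.7 |
|---|---|---|---|---|
| 6 | 2.52 | 2.54 | 2.20 | 1.81 |
| 5 | 2.85 | 2.88 | 2.48 | 2.05 |
| 4 | 3.36 | 3.38 | 2.93 | 2.41 |

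That is 13% narrower at 0.5 (for example 2.48 / 2.85 = 0.87), 28% narrower at 0.7, and up to 1% wider at 0. With arm-specific residual variances (REML, Satterthwaite degrees of freedom), the interval is 8–12% narrower at 0.5, 24–27% narrower at 0.7, and 2–6% wider at 0.

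A common-variance ANCOVA would appear to gain 20–25% and 34–38%, but 8 to 14 percentage points of that come from pooling variance across arms and not from Week 25.

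**Coverage of the primary pairs.** With SD 3.0 in the continued arms and 1.5 elsewhere:
- SAP rule: 94.1–94.7%
- HC2 ANCOVA: 94.0–94.6%
- common-variance ANCOVA: 92.2–92.8%

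Over all scenarios the HC2 version covers 94.0–95.5% and the arm-specific version 94.5–95.4%.

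**Variance pretest.** In 200,000 runs at SD 3.0 vs 1.5, the rule alone covers 94.6%, 94.5%, 94.2% for equal arms of 6, 5, 4. With 5 vs 11 patients it covers 90.5%, with the larger SD in the smaller arm. With the larger SD in the larger arm it covers 95.7–97.1%. In the seven-arm simulation, continued dose vs continued placebo covers:
- SD 3.0 vs 1.5: 90.1–91.6% (SAP rule), 93.2–94.1% (HC2 ANCOVA)
- SD 2.19 vs 1.93, the six-month values in Table 9-1: 93.5–94.4% (SAP rule), 94.4–95.4% (HC2 ANCOVA)

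**The case against.** **Little depends on it.** No hypothesis is tested (Protocol 9.4.2), Amendment 1 moved the main question to off-drug durability, and ±2.5 instead of ±2.85 still leaves the comparison imprecise. This stands, and it limits the weight of the point.

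**The gain rests on an unstated correlation and is only an average.** This also stands. At 0.5 the adjusted interval is wider than the planned one in 21%, 24% and 28% of pairs for n = 6, 5 and 4; at 0.3, in 40–45%. The simple pairwise ANCOVA gains 0–7% at 0.5. The 13% needs the slope to be estimated across all arms.

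**SAP 5.8.1 may mean change from Week 25.** Its endpoint list refers to Weeks 25 to 49, which could mean a change score or each visit in that range. SAP 3.4.2 and the endpoint definition are explicit about Week 49 values, so the reading here is the better one, but the sections should be reconciled. A change score would not settle the matter: its width ratio, √(2(1−ρ)), is 1.41 at ρ = 0, 1.00 at 0.5 and 0.77 at 0.7.

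**Redaction.** Parts of SAP 3.4.4 are blacked out, so an adjusted supportive analysis cannot be ruled out. The primary interval is unaffected.

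**Imbalance is already visible.** Week 25 SPPB is summarised by arm, and the t interval has close to nominal coverage for the primary pairs. That is correct: the claim concerns width only.

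**The low pretest coverage needs a 2:1 SD ratio.** The documents do not support such a ratio between arms, and at their own SDs the shortfall is small. That is fair, so the pretest remains a side point.

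**Other endpoints were not examined.** All scenarios use SPPB SDs, so the size of any gain for 6MWT, gait speed and lean mass is unknown.

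**Conclusion.** The point holds as a conditional loss of precision. The primary Population I interval ignores a valid pre-randomisation measurement of its own endpoint. With 4 to 6 patients per arm, one all-arm ANCOVA that does not assume a common variance would narrow it by about 8–13% at a correlation of 0.5 and 24–28% at 0.7. The cost is 0–6% in width if the correlation is near zero.

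This rests on an assumed correlation, on equal core arms, on 0–30% dropout and on an SD of 2.0. There is no bias, and the adjusted half-widths (1.81 points at best in the table) still exceed 1.0 point. The change is worth making because it is cheap, but the study's conclusions do not depend on it. The variance pretest is harmless for the primary pairs and a minor weakness against continued placebo.

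**What to change.** In SAP 3.4.2, 3.5.3.1 and 5.8.1:

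- Report Population I differences from one ANCOVA per endpoint, with extension arm as factor (both placebo codes as one arm) and that endpoint's own Week 25 value as covariate.
- Do not rely on a common residual variance. Use HC2 standard errors with Bell-McCaffrey degrees of freedom, or arm-specific residual variances with Satterthwaite degrees of freedom.
- Keep the raw Week 49 summaries by arm.
- Delete the variance pretest. Wherever an unadjusted t interval is still shown, always use the Satterthwaite form.
- Reword the endpoint list in 5.8.1 to agree with 3.4.2.

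The cost is SAP wording and a modest amount of programming; SAP 1.2 provides for changes before database lock. Always using Satterthwaite widens unadjusted intervals by about 2–5% for equal pairs, and by 4–9% against continued placebo when SDs are equal. Patients without a Week 25 value drop out of the ANCOVA, so their number should be reported.

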### 3.4.3 Handling of missing values/censoring/discontinuations

Summary statistics will be provided for observed data (no imputation in general, except special cases of the balance test described in section 1.3.2.2.2).

### 3.4.4 Supportive analysis

The same analysis will be performed on the PP analysis set [REDACTED] in two ways:

- [REDACTED]
- [REDACTED]
- [REDACTED]
- [REDACTED]

Proportions of patients being sarcopenic at Week 25 and Week 49 will be summarized by treatment, for population I and II separately. The criteria of being sarcopenic are from core study protocol inclusion criteria:

- Gait speed < 0.8 m/sec
- ASMI  $\leq 7.26 \text{ kg/m}^2$  for men and  $\leq 5.5 \text{ kg/m}^2$  for women, or for Asian countries  $\leq 7.0 \text{ kg/m}^2$  for men and  $\leq 5.4 \text{ kg/m}^2$  for women

## 3.5 Analysis of secondary [REDACTED]

The analyses described in this section will be based on FAS.

[figure not shown]
### 3.5.1 Variables

Secondary efficacy variables include:

- 6MWT at Week 49
- Gait speed at Week 49
- Total LBM and ASMI as measured by DXA at Week 49

- [REDACTED]

### 3.5.2 Descriptive statistics

Descriptive statistics (i.e. N, mean, SD, median, 25th percentile, 75th percentile, minimum and maximum (min/max not included for Interim Analysis), the number of non-missing observations, and 95% confidence interval), per treatment group and visit, will be provided for each continuous variable and each population separately.

Longitudinal plots (Mean +/- SE), by treatment of observed values vs time profile will be produced for each continuous variable and each population separately.

For Population II,  Lean body mass (LBM and ASMI) will be logarithmically

transformed before the analysis. The results of the analysis will be back-transformed from the log-scale before reporting.

[figure not shown]
### **3.5.3 Statistical model, hypothesis and method of analysis**

[figure not shown]
#### **3.5.3.1 6MWT, Gait speed, SPPB total score, total LBM and ASMI**

For population I, the 95% confidence interval will be provided for the difference between each continued BYM dose arm and corresponding placebo (switched from the same BYM dose arm) at each visit. 95% confidence interval will also be provided for the difference between each continued BYM dose arm and the placebo arm continued from the core study at each visit.

The confidence interval at Week 49 for SPPB total score between each continued BYM dose arm and corresponding placebo (switched from the same BYM dose arm) for population I is provided as the primary analysis. For population II, the summary statistics at Week 49 are provided as the primary analysis.

For population II, SPPB total score, 6MWT, Gait speed, total LBM and ASMI at Week 49 will be explored at final analysis using an analysis of variance model (ANCOVA) with treatment assigned in the core study [REDACTED] as fixed effects and Week 25 SPPB total score as covariate.

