The original study was designed to evaluate several questions i.e. how long the potential effect of 24 weeks of bimagrumab treatment would be maintained following treatment discontinuation and if a 48 weeks continuous treatment would provide additional benefit over a 24 weeks treatment period. The randomized withdrawal feature of the design reduced the sample size of each treatment arm with the risk of not being able to address the questions. Novartis with this amendment is removing this withdrawal randomization feature and is refocusing the study on one main question: how long the potentially observed effects after 24 weeks of treatment with bimagrumab will last once the treatment is discontinued? Therefore, all newly enrolled patients in this extension study will be followed off drug for a period of 24 weeks. As a consequence, the size of each treatment arm will remain as per study entry and not reduced as the withdrawal randomization would otherwise do. Questions no longer addressed by this study may be addressed at later stage of the bimagrumab clinical development program if they are still relevant.

Patient visits over the 24 weeks are reduced from seven to three since there is no need for on-site infusion every 4 weeks. This should substantially reduce patient burden and facilitate study acceptance. However in order to promote patients' engagement and adherence to the study, there is a required exercise program [REDACTED] and, monthly phone calls will be made to patients.

Patients active in the study upon implementation of this protocol amendment will remain on the original protocol visit schedule which reflects the randomized withdrawal design. This way all patients enrolled in this study prior to this protocol amendment will have a similar journey and even if the sample is small (estimated to approx. 45 patients) this sub-group of patients will provide valuable information on the effect of prolonged treatment for 49 weeks. At the time of this protocol amendment's implementation it is anticipated that 10 to 15 patients will be on going and will continue being dosed while newly enrolled patients will be followed off drug under a revised visit schedule.

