3.2 Rationale of study design

The aim of developing bimagrumab therapy in elderly adults with sarcopenia is to enable them to increase their physical function to a certain level that they could afterwards maintain without any support other than regular exercise and potentially vitamin D supplementation. This extension study is the natural follow-up of the patients treated for 24 weeks in the core study; it will evaluate the changes in physical function of this patient population over 24 week off-treatment period as well as assess the overall long-term safety of bimagrumab.

The study population will be comprised of men and women aged 70 years or older with sarcopenia who participated in the core study CBYM338E2202. Only patients who complete the 24 weeks of treatment in the core study will be eligible for this study given the purpose to evaluate the durability of 24-week therapy. Of the 293 patients expected to enroll in the core

study, it is expected that approximately 200 patients will be eligible and will agree to participate in this extension study.

Although patients enrolled under this amendment will not receive any investigational drug as part of this extension, they will have a standardized exercise program. The schedule of two to three exercise sessions per week will be maintained throughout the studies (core and extension) and will serve as a standard of care together with the vitamin D supplementation.

The code of the treatment received in the core study will remain blinded to sites and patients for the entire study duration including this extension study. This will avoid a potential reporting bias that patients and site staff may otherwise have when assessing physical function, mobility or reporting safety.

In line with the primary endpoint used in the core study, the extension will use the SPPB total score as the primary endpoint. The SPPB score and 4-meter gait speed have emerged as the predominant measures that characterize impaired lower extremity function in older adults in general and in those with sarcopenia and frailty ([Studenski et al 2014](#)).

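### SAP 3.5.3.1 and SAP 5.8.2 give the exploratory Population II ANCOVA different covariates for 6MWT, gait speed, total LBM and ASMI

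*SAP*

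**What the plan says.** SAP 3.5.3.1 names five Week 49 endpoints for Population II (SPPB total score, 6MWT, gait speed, total LBM and ASMI). It will explore them at the final analysis in one model, with treatment assigned in the core study "as fixed effects and Week 25 SPPB total score as covariate".

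SAP 5.8.2 lists the same five endpoints, with LBM and ASMI log-transformed, and gives the model terms as: "The endpoint value at extension baseline as a covariate, treatment arm (as assigned in the core study for population II"). It promises 95% confidence intervals for the bimagrumab-placebo differences. The purpose is put this way: "ANCOVA model is used to explore the durability of BYM338 on the following endpoints".

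SAP 5.4 fixes the vocabulary. Unqualified, "Baseline is defined as the core study baseline, for both populations". Of Week 25, the core end-of-treatment visit, it says "it is referring to a relative baseline to the extension study". The extension baseline in 5.8.2 is therefore Week 25.

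On status, SAP 3.5.3.1 states: "For population II, the summary statistics at Week 49 are provided as the primary analysis". Protocol 9.4.2 rules out formal hypothesis testing.

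On the question asked, the protocol's Amendment 1 rationale wants to know "how long the potentially observed effects after 24 weeks of treatment with bimagrumab will last once the treatment is discontinued", while Protocol 3.2 says of the extension that "it will evaluate the changes in physical function of this patient population over 24 week off-treatment period".

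**The concern.** A programmer cannot follow both sections for four of the five endpoints. Under 3.5.3.1, lean mass at Week 49 would be adjusted for a physical-performance score, although each patient's own Week 25 lean mass is available from the core end-of-treatment DXA scan. The choice affects precision and, if bimagrumab and placebo differ at Week 25, the estimate as well. Protocol 3.6 expects an increase in lean mass and better mobility on active drug, so a Week 25 difference is plausible. The model is run only at the final analysis. By then the sponsor's core team will have had treatment codes from the interim (Protocol 5.4), so the choice is better settled in writing beforehand.

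A secondary point concerns interpretation. Week 25 comes after 24 weeks of core treatment and 4 weeks after the last dose, so the covariate itself can carry a drug effect. A contrast adjusted for it is not the difference still present at Week 49. The SAP calls the result durability without saying which quantity is meant, and the two protocol statements quoted above point to different ones.

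**Working it through.** **Step 1. Compare the two rules.**

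| Week 49 endpoint | Covariate in SAP 3.5.3.1 | Covariate in SAP 5.8.2 | Same? |
|---|---|---|---|
| SPPB total score | Week 25 SPPB | Week 25 SPPB | yes |
| 6MWT | Week 25 SPPB | Week 25 6MWT | no |
| Gait speed | Week 25 SPPB | Week 25 gait speed | no |
| Total LBM (log) | Week 25 SPPB | Week 25 LBM | no |
| ASMI (log) | Week 25 SPPB | Week 25 ASMI | no |

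Redaction does not cause this. The blacked-out words in both sections sit among the fixed effects, and both covariate statements are legible. The plan states no figure that depends on the covariate, so there is none to reproduce.

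**Step 2. Precision.** Let r_own be the within-arm correlation of the Week 49 endpoint with its own Week 25 value, and r_cross its correlation with Week 25 SPPB. The documents give neither. Residual SD is proportional to sqrt(1 - r^2), so the half-width under 3.5.3.1 divided by that under 5.8.2 is approximately sqrt((1 - r_cross^2) / (1 - r_own^2)).

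- r_own 0.8, r_cross 0.3: sqrt(0.91 / 0.36) = 1.59
- r_own 0.6, r_cross 0.5: sqrt(0.75 / 0.64) = 1.08
- r_own 0.6, r_cross 0.7: sqrt(0.51 / 0.64) = 0.89

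The own-value covariate is more precise whenever r_own exceeds r_cross in size.

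**Step 3. Estimate.** For an endpoint with bimagrumab-placebo differences D25 and D49, the expected ANCOVA coefficient is D49 minus (within-arm slope on the covariate) × (arm difference in the covariate at Week 25). With no arm differences at Week 25, both models have the same expectation, D49. Otherwise they generally differ. As an illustration for 6MWT, assume a 25 m difference at both weeks, SD 80 m, SPPB SD 2 and a Week 25 SPPB difference of 1.0 point (Protocol 6.3.2 calls a change of 1.0 clinically relevant).

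- Own covariate: 25 - r_own × 25 = 12.5, 7.5 or 2.5 m at r_own 0.5, 0.7 or 0.9.
- SPPB covariate: 25 - r_cross × (80/2) × 1.0 = 13, 5 or -3 m at r_cross 0.3, 0.5 or 0.7.

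Either model can give the larger figure.

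**Step 4. What the Week 25-adjusted contrast measures.** With the endpoint's own Week 25 value as covariate, the coefficient is D49 - beta × D25, where beta is the within-arm slope (equal to the correlation when SDs are equal). For SPPB with D25 = 1.0 (assumed):

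| True D49 | beta 0.5 | beta 0.7 | beta 0.9 | Difference in raw change |
|---|---|---|---|---|
| 1.0 (fully retained) | 0.5 | 0.3 | 0.1 | 0 |
| 0.5 (half retained) | 0.0 | -0.2 | -0.4 | -0.5 |
| 0 (lost) | -0.5 | -0.7 | -0.9 | -1.0 |

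A large simulated sample with beta 0.7 and D25 = D49 = 1.0 gave 0.298, against 0.3 by formula.

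**Step 5. Scale against precision for SPPB.** Population II completers per arm: (200 - 45) × 0.7 / 4 = 27.1, assuming four equal arms and the protocol's 30% dropout. At 27 per arm, SD 2.0 and slopes 0.3 to 0.8, simulated half-widths of the Week 25-adjusted difference are 1.05 to 0.65 points. At 40 per arm they are 0.86 to 0.53. The gap beta × D25 is 0.15 to 0.40 points if D25 = 0.5, 0.30 to 0.80 if D25 = 1.0, and zero if D25 = 0.

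**The case against.** The strongest reply is that the documents suggest a working hierarchy. SAP 4 refers the reader to Appendix 16.1.9 for details, and SAP 5 is that appendix, so 5.8.2, with its endpoint-by-endpoint covariates and log scale, looks like the operative text. Section 3.5.3.1 then reads as SPPB wording applied to all five endpoints. This is a sensible reading and supports the direction of the fix. It is not a precedence rule, however: SAP 5.1 describes the appendix only as an addition to the report text.

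On interpretation, the reply is that outcome, contrast, covariate and interval are all stated, and that a contrast conditional on Week 25 suits an off-drug study. That largely stands. The interval is valid for its own target, covering it about 95% of the time in simulation. By-arm Week 49 means with confidence intervals (SAP 3.4.1 and 3.5.2) already show the level reached. What remains is a labelling matter, and it applies under either covariate, since Week 25 SPPB is also measured after treatment.

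A reader might also infer that Population II has no planned contrast for the retained Week 49 effect. The documents do not support that. Parts of SAP 3.4.4, 3.5.4 and 3.8 and the text after 5.8.2 are redacted, and such a contrast may be planned there.

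**Conclusion.** The covariate contradiction is real, legible and confined to 6MWT, gait speed, total LBM and ASMI. Severity is minor: the model is exploratory, the protocol's analysis section does not contain it, nothing is formally tested, and the primary by-arm Week 49 summaries for Population II do not depend on it.

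It is tempting to conclude that following 3.5.3.1 always widens the interval, or always gives the larger effect. Neither follows. The half-width ratio is 1.59 or 0.89 depending on the assumed correlations. The estimates differ in expectation only if there is a Week 25 arm effect, and then in either direction. Nor is the Week 25-adjusted analysis biased: it estimates D49 - beta × D25, which is baseline-adjusted change after end of treatment. The risk is that a result labelled durability is read as the effect still present at Week 49. All sizes given rest on assumed correlations, slopes and Week 25 differences, because the documents supply none.

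**What to change.** Change SAP 3.5.3.1 to match 5.8.2, so that each endpoint is adjusted for its own Week 25 value, with LBM and ASMI on the log scale for both outcome and covariate. In both sections, label the resulting contrast as baseline-adjusted change after end of treatment.

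If the redacted text does not already plan one, a Week 49 bimagrumab-placebo difference with 95% confidence interval can be added for the retained effect. It should be adjusted for the endpoint's core-study baseline, which SAP 5.4 already defines. The report should note that only patients who completed core treatment could enter, so this is not a fully randomised comparison.

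The first change costs a few words in the SAP. The optional contrast needs core-baseline values, linked through the unchanged patient number, and a small amount of extra programming. No new patient data are required.
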